## **8.5.7 Specific Safety Management Guidelines**

### **8.5.7.1 Anemia, Blood Cross-matching, and Packed Red Blood Cell Transfusion Procedures**

Magrolimab binds to RBCs and leads to erythrophagocytosis. In clinical studies, anemia is the most common treatment-related AE and is typically manifested as a decline in Hgb observed in the first 1 to 2 weeks of treatment. Subjects with low baseline Hgb level, especially those with cardiac history, should be monitored closely after initial administrations of magrolimab as preexisting anemia could be exacerbated. In general, a Hgb level of at least 9.5 g/dL or higher for subjects with cardiac comorbidities prior to the first magrolimab dose is recommended. Hgb  $\geq 9$  is required prior to the first two doses in priming and repriming of magrolimab. Red blood cell transfusions are permitted prior to study treatment to ensure adequate Hgb level. This, coupled with anemia from other causes in participants with cancers, means that care has to be taken with RBC cross-matching and packed RBC transfusions. There is a possibility that treatment with magrolimab may obscure assessment of RBC phenotyping, although this has not been observed in the subjects treated to date.

Prior to initiation of magrolimab, extended RBC phenotyping or genotyping for minor antigens, type and screen (ABO/Rh), and DAT will be performed for each subject as described in Section 5.3.3. This, together with using the prior phenotype, will facilitate allocation of properly matched blood, should a blood transfusion be warranted.

### **8.5.7.2 Management of Infusion-related Reactions**

Infusion-related reactions are defined by the National Cancer Institute Common Terminology Criteria for Adverse Events (NCI CTCAE), Version 5.0 (under the category “General disorders and administration site conditions”) as “a disorder characterized by adverse reaction to the infusion of pharmacological or biological substances” (Section 10.5). For the purposes of this study, the time frame for infusion-related reaction assessment is the 24-hour period beginning from the start of the infusion. Premedication use described in Section 6.5 will be used to manage infusion-related reactions preemptively.

Recommendations for the management of infusion-related reactions are provided below.

- For Grade 1 infusion-related reactions, described as mild transient reaction, infusion interruption is not indicated, and intervention not indicated.
  - Remain at bedside and monitor participant until recovery from symptoms.
- For Grade 2 infusion-related reaction, infusion interruption is indicated, but participant responds promptly to symptomatic treatment (eg, antihistamines, nonsteroidal anti-inflammatory drugs, narcotics, corticosteroids, IV fluids), and prophylactic medications are indicated for  $\leq$ 24 hours:
  - Stop the magrolimab infusion, begin an IV infusion of normal saline, and consider treating the participant with diphenhydramine 50 mg IV (or equivalent) and/or 500 mg to 750 mg of oral acetaminophen.
  - Remain at bedside and monitor participant until resolution of symptoms.
  - Corticosteroid therapy may also be given at the discretion of the investigator.
  - If the infusion is interrupted, wait until symptoms resolve, then restart the infusion at 50% of the original infusion rate.
  - If no further complications occur after 1 hour ( $\pm$  10 minutes), the rate may be increased to 100% of the original infusion rate. Monitor the participant closely.
  - If symptoms recur, stop infusion and disconnect participant from the infusion apparatus. No further magrolimab will be administered at that visit.
  - Premedications should be considered before any future infusions.
  - The amount of magrolimab infused must be recorded on the eCRF.
  - Participants who experience a Grade 2 infusion-related reaction during the postinfusion observation period that does not resolve to  $\leq$  Grade 1 during that time should be observed until the AE resolves or stabilizes, with vital sign measurements as medically indicated for the management of the AE.
- For Grade 3 or Grade 4 infusion-related reaction, where Grade 3 is described as prolonged infusion-related reactions (eg, not rapidly responsive to symptomatic medication and/or brief interruption of infusion), or recurrence of symptoms following initial improvement, or where hospitalization is indicated for other clinical sequelae (eg, renal impairment, pulmonary infiltrates) and Grade 4 is described as having life-threatening consequences and where urgent intervention is indicated.
  - Immediately discontinue infusion of magrolimab.
  - Begin an IV infusion of normal saline and consider treating the participant as follows: Administer bronchodilators, epinephrine 0.2 mg to 1 mg of a 1:1000 solution for subcutaneous administration or 0.1 mg to 0.25 mg of a 1:10,000 solution injected slowly

for IV administration and/or diphenhydramine 50 mg IV with methylprednisolone 100 mg IV (or equivalent), as needed.

- The participant should be monitored until the Investigator is comfortable that the symptoms will not recur.
- Participants who have Grade 4 infusion-related reactions occurring with the first dose (priming dose) will be permanently discontinued from study treatment.
- Participants who experience Grade 3 or 4 infusion-related reactions must be given premedication prior to subsequent doses. In this setting, premedication with oral acetaminophen (650 mg to 1000 mg), oral or IV diphenhydramine (25 mg to 50 mg), and IV dexamethasone (4 mg to 20 mg), or a comparable regimen, is recommended for the subsequent 2 doses. Continued premedication with corticosteroids beyond these 2 doses may be administered at the discretion of the treating physician.
- Participants who receive premedication and still experience a Grade 3 or 4 infusion-related reaction will be permanently discontinued from the study treatment.
- For anaphylaxis, investigators should follow their institutional guidelines for treatment.
- All participants with Grade 3 or greater infusion-related reactions will be observed until the AE resolves or stabilizes, with vital sign measurements and additional evaluations as medically indicated for the management of the AEs.

## 9.0 STATISTICAL CONSIDERATIONS

### 9.1 Sample Size Determination

The CR rate with HMA monotherapy varies between studies and depends on severity of disease with an estimated overall range of approximately 10% to 20%. In Study ASTX727-02, for higher-risk MDS (IPSS-R >3) subjects, the observed CR rate with oral decitabine/cedazuridine was 22% (95% confidence interval [CI] of 14% to 32%).

The combination of magrolimab plus azacitidine seems promising with better efficacy compared to azacitidine monotherapy, including a 50% CR rate, objective response rate of 92%, with an acceptable safety profile, suggesting that this combination offers advantages beyond HMA monotherapy ([Garcia-Manero et al 2020](#)). Assuming treatment of higher-risk MDS subjects with HMA oral decitabine and cedazuridine or with azacitidine is similar and that the combination of HMA oral decitabine/cedazuridine with magrolimab will result in a CR rate of approximately 40%, a sample size of approximately 100 subjects will allow for a greater than 80% power to rule out an HMA response rate of 20% (ie, lower bound of the exact 95% CI for the response rate will be greater than 20%). In addition, assuming that the response rate for this study will be approximately 40%, a sample size of approximately 100 subjects will allow for 80% power to estimate a CI with half-width of approximately 10%. This sample size represents a preliminary estimate of the study size, however, the final sample size for the study may be revised based on the final response rate to be observed in the Phase 3 Magrolimab ENHANCE study.

## 9.2 Analyses Sets

For purposes of analysis, the following populations are defined:

**Table 15: Analysis Populations**

Population	Description
Enrolled	All subjects who sign an ICF and meet all eligibility criteria as assessed by the investigator and sponsor.
Efficacy	All subjects who receive any study treatment.
Safety	All subjects who receive any study treatment.
PK	All subjects who have received study treatment and for whom PK samples were collected and successfully analyzed.

ICF=informed consent form; PK=pharmacokinetic

## 9.3 Statistical Analyses

The statistical analysis plan (SAP) will be finalized prior to any efficacy assessment (first interim analysis for futility), and it will include a technical and detailed description of the statistical analyses described in this section. This section is a summary of the planned statistical analyses of the most important endpoints including primary and key secondary endpoints.

### 9.3.1 General Considerations

All efficacy and safety endpoint parameters will be summarized descriptively. Continuous efficacy and safety endpoints will be summarized using the mean, standard deviation, median, minimum, and maximum, 25 and 75 percentiles). Frequency distributions (counts and percentages) will be used to summarize categorical endpoints.

The primary efficacy analysis will be performed using a 2-sided 0.05 significance level. No adjustments for multiple endpoints is planned.

It is anticipated that statistical summaries will be performed using SAS Version 9.4 or higher (SAS Institute, Inc., Cary, NC, USA) or higher. Additional software may be used to produce graphics and for statistical methodology not available in SAS.

### 9.3.2 Primary Endpoint(s)

The primary efficacy endpoint for this study is the proportion of subjects who achieve CR. Response rate will be based on the investigator assessment for all treated subjects. Exact Clopper-Pearson 95% CI will be presented.

The analysis of duration of CR, ORR, OS, and PFS will be conducted using the Kaplan-Meier method based on subjects who achieved CR. Median duration of CR will be estimated with its 95% CI for each treatment arm based on the Kaplan-Meier method. For the time-to-event

endpoints of the duration of CR and DOR will be based on subjects who achieved ORR. The median duration will be estimated with its 95% CI for each treatment arm.

Analysis for all secondary efficacy endpoints will also be performed by pre-specified subgroups. Details of this analysis will be presented in the SAP.

No formal hypothesis testing will be conducted for any key secondary endpoint.

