### 3.0 OBJECTIVES AND ENDPOINTS

Objectives	Endpoints
Primary	

To evaluate preliminary safety and efficacy of oral decitabine/cedazuridine in combination with magrolimab.

	

Adverse events graded according to NCI CTCAE, Version 5.0 (Section 10.5), DLTs, and CR rate.

Secondary	

To evaluate the PK profile of oral decitabine/cedazuridine and magrolimab.

	

Concentration versus time and PK parameters.

To evaluate other clinical efficacy of oral decitabine/cedazuridine and magrolimab.

	

ORR, rate of HI, duration of PFS, LFS, undetectable disease assessed by MRD, DOR, and OS.

To evaluate efficacy and safety by prespecified subgroups (eg, IPSS-M, p53 status).

	

Safety and efficacy based on molecular features (eg, IPSS-M score, p53 status).

CR=complete response; DLT=dose-limiting toxicity; DOR=duration of response; HI=hematologic improvement; IPSS-M=Molecular International Prognostic Scoring System for myelodysplastic syndromes; LFS=leukemia-free survival; MRD=minimal residual disease; NCI CTCAE=National Cancer Institute Common Terminology Criteria for Adverse Events; ORR=overall response rate; OS=overall survival; PFS=progression-free survival; PK=pharmacokinetic(s)

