### 4.0 STUDY DESIGN

#### 4.1 Overall Design

This is a Phase 2, open-label, multicenter, non-randomized interventional study to evaluate the safety, efficacy, and PK of oral decitabine/cedazuridine when given in combination with magrolimab for the treatment of subjects with previously untreated intermediate- to very high-risk MDS. Subjects with higher-risk MDS (IPSS-R  $\geq 3.5$ ) will be screened for participation with the goal of obtaining approximately 100 subjects who are evaluable, those subjects receiving one or more dose of study treatment, for the primary study endpoint. The first 6 to approximately 18 subjects enrolled will be evaluated for dose-limiting toxicities (DLTs) during the first 2 cycles of oral decitabine/cedazuridine and will be used to confirm the dosing for oral decitabine/cedazuridine in combination with magrolimab. In this protocol, a cycle is defined as a

cycle of oral decitabine/cedazuridine, which is normally 28 days. Dose-limiting toxicities are defined in Section 8.5.6.

The primary analysis of the CR rate will be conducted approximately 8 months after enrollment of approximately 100 subjects has occurred. Participation will include screening, treatment, and follow-up. The screening period will last up to 21 days before the first dose of study treatment, during which time the participant's eligibility and baseline characteristics will be determined. Subjects will receive study treatment per the dosing schedule in [Table 3](#) and [Table 4](#). Study treatment may be continued until disease progression (including treatment failure by the International Working Group [IWG] 2006 criteria or relapse after PR/CR), or unacceptable toxicities occur, the subject is withdrawn from study treatment, or the sponsor stops the study. In case subjects choose to discontinue the study treatment due to reasons other than disease progression, eg, voluntary withdrawal, subjects will be followed up for response assessments until documented disease progression occurs. For subjects who stop receiving the study treatment to receive a stem cell transplant (SCT), follow-up for response assessment and collection of SOC BM biopsy/aspirate results will continue until documented disease progression occurs or start of new anticancer therapy, whichever occurs first. Then subjects will be observed for survival until death, withdrawal of consent, or the end of the study, whichever occurs first.

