### **8.3.2 Long-term Follow-up**

Beginning 3 months after the 30-day Safety Follow-up visit (for subjects who permanently discontinued treatment), subjects will be followed in long-term follow-up for health status information, which will be gathered every 3 months ( $\pm 2$  weeks) until death, the subject withdraws consent, the subject is lost to follow-up, or the study ends, whichever occurs first. Long-term follow-up may be accomplished through a telephone call to the subject or next of kin, contact with the local treating physician, or medical record review. If the subject did not have disease progression prior to treatment discontinuation, the absence of disease progression should be monitored according to standard practice during long-term follow-up contact. For subjects who discontinued treatment before documented disease progression and have a telephone visit, they should be asked if they have had disease progression (bone marrow blast count  $\geq 5\%$  and MDS conversion to AML) or any transfusion requirements since last contact. Follow-up contact will also permit BM biopsy reports to be obtained from subjects that discontinue treatment to receive an SCT, allowing efficacy to be followed at this stage. The investigator or designee should record the subject's survival status in the eCRF. Date of death may be collected and recorded in the EDC system from public sources in cases of subjects who withdraw consent or who are lost to follow-up. In the event of death, a death form detailing the primary cause of death must be completed for the subject.

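### Section 9.3.2 restricts the Kaplan-Meier analysis of OS and PFS to complete responders, leaving out about 60 of 100 treated subjects at the planned 40% CR rate

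*Combined protocol and SAP*

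**What the plan says.** The second paragraph of Section 9.3.2 gives the only analysis set specific to OS and PFS: "The analysis of duration of CR, ORR, OS, and PFS will be conducted using the Kaplan-Meier method based on subjects who achieved CR". The same paragraph continues "Median duration of CR will be estimated with its 95% CI for each treatment arm", and it mentions treatment arms a second time for the median durations. It then gives a second, different set for duration of CR, namely overall responders. The next paragraph adds "Analysis for all secondary efficacy endpoints will also be performed by pre-specified subgroups".

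Elsewhere the document points to all treated subjects:

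- Table 15 (Section 9.2) defines the Efficacy population as "All subjects who receive any study treatment". The CR rate in Section 9.3.2 itself also uses all treated subjects.
- Section 3.0 lists the secondary efficacy endpoints as "ORR, rate of HI, duration of PFS, LFS, undetectable disease assessed by MRD, DOR, and OS", with no condition on response.
- Section 4.1 says of follow-up: "Then subjects will be observed for survival until death, withdrawal of consent, or the end of the study, whichever occurs first". Section 8.3.2 says "The investigator or designee should record the subject's survival status in the eCRF". Neither depends on response.

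Section 9.3 says the SAP will contain "a technical and detailed description of the statistical analyses described in this section".

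**The concern.** OS and PFS are there to describe how treated subjects fare on the combination. A set defined by CR is defined by something that happens after treatment starts. A subject who dies or progresses before CR cannot enter it, so the curves and medians would describe complete responders only. The IPSS-M and p53 subgroup displays of OS and PFS would carry the same selection, because the subgroup sentence covers every secondary efficacy endpoint.

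There is a second problem if time is measured from first dose. Each CR subject must have been event-free up to the date of CR, so that interval is guaranteed and pushes the curve upward even if CR has no effect on survival. If time is measured from CR, this inflation disappears but the selection remains. The protocol does not state the time origin.

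The practical risk is that a responder-only median is reported as the study's OS or PFS and set beside an all-patient figure, such as the background OS of about 18 months on hypomethylating agents (HMAs) quoted in Section 2.1.

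**Working it through.** **The plan's own design figures.** Section 9.1 assumes about 100 treated subjects, a CR rate of 40%, and success if the exact 95% lower bound exceeds 20%. The smallest count meeting that is 29 of 100 (lower bound 20.4%). At a true rate of 40% the power is 99.2%, consistent with the stated figure of more than 80%. At 40 of 100 the exact interval is 30.3% to 50.3%, a half-width of 9.97 points against the stated 10 or so. So 100 subjects and 40% are the right planning inputs.

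**Subjects left out of OS and PFS.** Number left out = 100 × (1 − CR rate).

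| CR rate | Source | Left out per 100 |
|---|---|---|
| 40% | planning value, Section 9.1 | 100 × 0.60 = 60 |
| 20% | HMA rate to be ruled out, Section 9.1 | 100 × 0.80 = 80 |
| 50% | magrolimab plus azacitidine, Section 2.2 | 100 × 0.50 = 50 |

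At a true rate of 40%, the binomial 95% range for the number left out is 50 to 69.

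**Guarantee time (illustration, only if time runs from first dose).** Assume a constant hazard λ, no effect of CR on survival, and every CR recorded at one time T. A subject is in the CR set only if event-free at T, so for t > T

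P(S > t | S > T) = exp(−λ(t − T)).

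The CR-only median is therefore the all-treated median plus T, whatever λ is. With 28-day cycles, Day 1 of cycle c falls at T = 28 × (c − 1) / 30.4375 months:

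- Cycle 2 Day 1: 28 / 30.4375 = 0.92 months.
- Cycle 10 Day 1: 252 / 30.4375 = 8.28 months.

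Taking the 18-month background OS from Section 2.1 as the all-treated median:

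- The CR-only median is 18 + 0.92 = 18.9 months or 18 + 8.28 = 26.3 months.
- 12-month survival in all treated subjects is 2^(−12/18) = 63%.
- 12-month survival in the CR set is 2^(−(12 − 0.92)/18) = 65% or 2^(−(12 − 8.28)/18) = 87%.

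The document gives no PFS median. At an assumed 12 months, the CR-only median would be 12.9 or 20.3 months.

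A simulation of 2,000,000 subjects under the same assumptions gave CR-only medians of 18.93 and 26.26 months from first dose (all-treated median 18), and 12.92 and 20.29 months (all-treated median 12). Measured from CR, it gave 18.01, 17.98, 12.00 and 12.01 months, so no shift.

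The two values of T are examples, not bounds. Section 8.3.1 has marrow assessed every cycle until marrow CR, whereas footnote s of Table 1 has it at Cycles 3, 5 and 7 and then every third cycle.

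**The case against.** **No two sentences contradict each other outright.** Table 15 defines populations but assigns no endpoint to them, and the follow-up sections concern data collection, which is compatible with any analysis set. That is correct. The conflict is with the definition of the only efficacy population and with the purpose of the endpoints. It is still real: the one sentence that does assign a set to OS and PFS assigns the wrong one.

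**The paragraph is visibly garbled and would not be followed literally.** It puts ORR, a proportion, under Kaplan-Meier. It gives duration of CR two different sets. It also refers to treatment arms in a study that Table 8 labels single-arm and Section 4.2 describes as having no comparator. A drafting slip is indeed the likely explanation, but that strengthens the case for rewriting the paragraph before anyone programs from it.

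**The SAP may put it right.** It may; Section 9.3 calls itself a summary, and the SAP is to be final before any efficacy assessment. But Section 9.3 describes the SAP as elaborating these analyses, and nothing supplied says it will depart from them. Whether the restriction would reach an actual output cannot be settled from the document.

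**The guarantee-time figures rest on strong assumptions.** This largely stands. The time origin is not stated, and a single time of CR is artificial. Having every CR recorded at Cycle 10 Day 1 sits poorly with a primary analysis about 8 months after enrolment (Section 4.1). CR at Cycle 7 Day 1 would give 168 / 30.4375 = 5.5 months, hence a median of 23.5 months instead of 26.3. The assumption that CR has no effect also means these figures do not measure the prognostic selection of responders. They show direction and rough scale only. The count of subjects left out needs none of these assumptions.

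**The consequence is limited.** Agreed: no formal testing is planned for key secondary endpoints, and survival data are collected whatever the response.

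**Conclusion.** The concern holds. As written, Section 9.3.2 yields responder-only OS and PFS, leaving out about 60 of 100 treated subjects at the planned 40% CR rate (80 at 20%, 50 at 50%). This rests only on the wording and the plan's own rates.

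The upward shift in the medians is conditional. It equals the time to CR if time runs from first dose with a constant hazard and no CR effect (0.9 months at Cycle 2 Day 1, 8.3 months at Cycle 10 Day 1), and it is zero if time runs from CR.

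This should be fixed, but it touches no decision rule: the primary CR analysis, sample size, futility rule and toxicity boundary stand as they are.

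**What to change.** Rewrite the second paragraph of Section 9.3.2 and carry the same text into the SAP:

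- OS and PFS: Kaplan-Meier from first dose in the Efficacy population (all treated subjects), with the subgroup displays on the same basis.
- ORR: a proportion with an exact 95% interval in all treated subjects.
- Duration of CR: in subjects with CR. DOR: in overall responders. This also removes the double definition for duration of CR.
- Delete both references to treatment arms.

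The cost is protocol and SAP wording only; no further data or subjects are needed. The reported OS and PFS medians may be less favourable than CR-only medians would have been. Because the study is open-label, the change should be made before efficacy results are examined, so that it cannot look data-driven.
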